### **7.3.3 Medical History**

General medical history will be listed by subject and pretreatment events will be tabulated.

### **7.3.4 Prior therapy**

The following will be summarized:

- Number of subjects by type of prior therapy received (excluding preparative regimen for ASCT):
  - Immunotherapy by Monoclonal Antibodies
  - Steroid
  - Chemotherapy – Anthracyclines
  - Chemotherapy – Other than Anthracyclines
  - Kinase Inhibitors
  - Immunomodulatory Derivatives
  - Radioimmunotherapy
  - Other
- Number of subjects per type of regimen for first and second lines of therapy (e.g. R-CHOP, ICE)
- Number of subjects by type of regimen (BEAM, CBV, Other) received for preparation to ASCT (for ASCT failed cohort only)
- Number of prior systemic regimen received (0, 1, 2, 3, ≥4), excluding preparative regimen for ASCT subjects
- Best response to most recent prior regimen (CR vs PR vs SD vs Relapse/PD vs Unable to Determine vs Not reported)
- Best response before transplant (for ASCT failed cohort)
- Best response to ASCT (for ASCT failed cohort)

- Best response to regimen post ASCT (for ASCT failed cohort)
- Time from completion of most recent prior regimen to treatment (< 3, 3 - 6, > 6 months)
- Prior radiotherapy (yes or no)

Other Prior therapy:

- Prior/current non-study medication classified by anatomic and therapeutic classes. Medication will be reported using the generic name. A listing by subject will also be provided.

### 7.3.5 Baseline Examinations

Percentage of subjects with abnormal baseline physical examination will be tabulated by examination criteria.

## 7.4 Extent of Exposure

Analyses in this section will be performed in all treated subjects for the 2 cohorts separately and on the pooled population.

### 7.4.1 Administration of Study Therapy

The following parameters will be summarized (descriptive statistics):

- Relative dose intensity (%) using the following categories: < 50%; 50 - < 70%; 70 - < 90%; 90 - < 110%; ≥ 110%.
- Number of doses received (summary statistics)
- Cumulative dose
- Duration of treatment: duration of treatment will be presented using a Kaplan-Meier curve whereby the last dose date will be the event date for subjects who discontinued study therapy. Subjects who are still on study therapy will be censored on their last dose date. Median duration of treatment and associated 95% CI will be provided.
- A by-subject listing of dosing of study medication (record of study medication, infusion details, dose change) and a listing of batch number will be also provided.

**Table 7.4.1-1: Administration of study therapy: definition of parameters**

nivolumab	
Dosing schedule per protocol	3 mg/kg every 2 weeks
Dose	Dose(mg/kg) is defined as Total Dose administered (mg)/Most recent weight (kg). Dose administered in mg at each dosing date and weight are collected on the CRF.
Cumulative Dose	Cum dose (mg/kg) is sum of the doses (mg/kg) administered to a subject during the treatment period.
Relative dose intensity (%)	$\text{Cum dose (mg/kg)} / [ (\text{Last dose date} - \text{Start dose date} + 14) \times 3 / 14 ] \times 100$
Duration of treatment	Last dose date - Start dose date +1

## **7.4.2 Modifications of Study Therapy**

### **7.4.2.1 Dose delays**

Treatment may be delayed for up to a maximum of 6 weeks from the last dose. A dose will be considered as actually delayed if the delay is exceeding 3 days (i.e., greater than or equal to 4 days from scheduled dosing date). Length of delay is defined as (duration of previous cycle in days - 14). Dose delays will be divided into following categories: 4 - < 8 days, 8 - < 15 days, 15 - < 42,  $\geq$  42 days. Reason for dose delay will be retrieved from CRF dosing pages.

The following parameters will be summarized:

- Number of subjects with at least one dose delayed, number of dose delayed per subject, Length of Delay and Reason for Dose Delay

### **7.4.2.2 Infusion Interruptions and Rate Changes**

The following parameters will be summarized:

- Number of subjects with at least one dose infusion interruption, number of infusion interruptions per subject and the reason for interruption.
- Number of subjects with at least one IV infusion rate reduction, number of IV infusion rate reduction per subject and the reason for reduction

### **7.4.2.3 Dose Reductions/Escalation**

There will be no dose escalations or reductions of nivolumab allowed.

[REDACTED]

## **7.5 Efficacy**

Unless otherwise specified analyses from this section will be produce by cohort separately.

### **7.5.1 Primary endpoint of ORR (IRRC-assessed)**

The IRRC-assessed ORR (using 2007 revised International Working Group Criteria for Malignant Lymphoma criteria) will be summarized on the all subjects treated population by a binomial response rate. The method proposed by Atkinson and Brown will be used to estimate the CI for the ASCT-failed cohort if the responders at interim analysis are above the critical value, which is 8 responders. This confidence interval takes into account the group sequential nature of the two

stage modified Simon design. The two-sided 90% CI will be presented, corresponding to the nature of the 1-sided 5% alpha from the modified Simon design. In addition, per protocol, the two-sided 95% CI will be presented. However, if the responders are below the critical value and we don't stop the study, we are no longer following the two-stage design. The two-sided confidence intervals for binomial proportions will be derived using the Clopper-Pearson method.

The Clopper-Pearson method will be used to estimate the two-sided 95% CI for the ASCT ineligible cohort, as well as 90% and 95% confidence intervals for ORR at interim analysis (IA).

In the ASCT failed cohort, the null hypothesis will be rejected if 25 or more responses are observed in 90 treated subjects at the final analysis (FA). In case not exactly 90 treated subjects are available, success will be referenced to a 2-sided 90% CI lower bound greater than 20%.

Success of the ASCT ineligible cohort will be referenced to a 2-sided 95% CI lower bound greater than 17.3%.

BOR will be summarized by response category.

Summary statistics of time to objective response will be provided for subjects who achieve PR or CR, as assessed by the IRRC. CR requires confirmation by PET. To assess tumor response kinetics, time to response will also be analyzed using the KM methodology for all treated subjects. Kaplan-Meier curve will represent the cumulative rate of response over time. For the non-responders, time to response will be censored at the maximum time of response + 1 day of all subjects. Cumulative Response Rates will be tabulated for Week 9, Month 4, 6, 8, 12 and 18, and overall Response Rate will be provided.

#### **7.5.1.1 ORR Subgroups**

To assess consistency of ORR, IRRC-assessed ORR (primary analysis) will be summarized for the following subgroups (for subjects in the ASCT failed cohort only):

- Age (<65, ≥ 65, ≥ 65 and < 75, ≥ 75)
- Region (US/Canada, Europe, Rest of the world).
- Gender (Male, Female)
- Race (white, black, Asian, and other)
- Smoking status (yes/no)
- ECOG (0, 1)
- Time from the initial diagnosis to transplant (< 1 year, 1 - < 2 year, 2 - < 3 year, 3 - < 4 year, 4 - < 5 year, ≥5 year)
- Number of prior therapies (1, 2, 3, ≥4) excluding preparative regimen
- Time from most recent prior regimen to first dose of nivolumab (< 3 months, 3 - 6 months, >6 months)
- Refractory, Relapsed Lymphoma
- DLBCL, Transformed Lymphoma

- IPI Score (0,1, 2, 3, 4,...)

Categories including less than 5 subjects may be collapsed. Analyses of subgroups of less than 5 subjects may not be provided.

### **7.5.1.2 Sensitivity analyses for ORR**

- As sensitivity analysis, a summary of IRRC-assessed ORR based on response evaluable subjects instead of all treated subjects will also be presented. Clopper Pearson 95% CI will be used in this analysis.
- To assess concordance between IRRC (primary analysis) and investigator assessments, BOR categories (responders versus non-responders versus non-evaluable or no evidence of disease versus not reported) will be cross-tabulated by assessment type (Investigator vs IRRC). Concordance Rate of Responders will be computed as the frequency with which Investigator and IRRC agree on classification of a subject as responder/non responder as a proportion of the total number of subjects assessed.

### **7.5.2 Secondary Endpoint of Duration of Response (IRRC-assessed)**

The DOR will be summarized by cohort for subjects who achieve PR or CR as determined by IRRC using KM product-limit method. Two-sided, 95% confidence intervals for median DOR will be constructed based on log-log transformation. Range of DOR will also be presented. In addition, the percentage of responders still in response at different time points (3, 6 and 12 months) will be presented based on the DOR KM plot.

Duration of stable disease will also be estimated using KM product-limit method for subjects with SD as best response. Two-sided, 95% confidence intervals for median duration of SD will be computed.

### **7.5.3 Secondary Endpoint of Complete Remission Rate and Duration (IRRC-assessed)**

IRRC-assessed CRR will be summarized by cohort by a binomial response rate and its corresponding two-sided 95% exact CIs using the Clopper-Pearson method.

To further characterize CRR, the duration of CR will be summarized by cohort for subjects who achieve CR as determined by IRRC using KM product-limit method. Two-sided, 95% confidence intervals for median duration of CR will be constructed based on log-log transformation. Range of duration of CR will also be presented.

### **7.5.4 Secondary Endpoint of Partial Remission Rate and Duration (IRRC-assessed)**

IRRC-assessed PRR will be summarized by cohort by a binomial response rate and its corresponding two-sided 95% exact CIs using the Clopper-Pearson method.

To further characterize PRR, the duration of PR will be summarized by cohort for subjects who achieve PR as determined by IRRC using KM product-limit method. Two-sided, 95% confidence intervals for median duration of PR will be constructed based on log-log transformation. Range of duration of PR will also be presented.

### **7.5.5 Secondary Endpoint of Progression Free Survival (IRRC-assessed)**

IRRC-assessed PFS will be summarized descriptively by cohort using the Kaplan-Meier (KM) product-limit method. Median values of PFS, along with two-sided 95% CIs (based on the log-log transformation), will also be calculated.

The source of progression (death vs. progression) will be summarized.

The status of subjects who are censored in the PFS Kaplan-Meier analysis will be tabulated using following categories:

- Received subsequent anti-cancer therapy (Stem Cell Transplant, other)
- Still on-treatment
- Progression-free in follow-up
- Off-study: (lost to follow-up, withdrew consent, other).

KM curve of PFS will be generated. PFS rates per IRRC at 6 month will be estimated using KM estimates on the PFS curve. PFS rates at 6, 12, 18 and 24 months may also be estimated depending on whether minimum follow-up will be longer than timepoint to generate the rate. Associated two-sided 95% CIs will be calculated.

Subject listings of PFS will be produced.

#### **7.5.5.1 Sensitivity analyses of PFS**

Sensitivity analyses of PFS based on IRRC assessment will also be performed using the following modification of PFS primary definition.

- PFS accounting for assessment after subsequent therapy: PFS will be defined similarly to the primary definition except that events (progression or death) and tumor assessments that occurred after subsequent anti-cancer therapy will be considered (no time point truncation).

### **7.5.6 Secondary Endpoint of Objective Response Rate (Investigator-assessed)**

Investigator-assessed ORR will be summarized by cohort by a binomial response rate and its corresponding two-sided 95% exact CIs using the Clopper-Pearson method.

Investigator-assessed BOR will be summarized by response category.

Summary statistics of time to objective response will be provided for subjects who achieve PR or CR, as assessed by the Investigator. CR requires confirmation by PET. To assess tumor response kinetics, time to response will also be analyzed using the KM methodology for all treated subjects. Kaplan-Meier curve will represent the cumulative rate of response over time. For the non-responders, time to response will be censored at the maximum time of response + 1 day of all subjects. Cumulative Response Rates will be tabulated for Week 9, Month 4, 6, 8, 12 and 18, and overall Response Rate will be provided.

[Redacted text block]

[Redacted text block]

[Redacted text block]

## **7.6 Safety**

All analyses from the Core Safety SAP will be produced for the ASCT-failed and ASCT ineligible cohorts pooled and for the ASCT-failed cohort separately.

### **7.6.1 Deaths**

See Core Safety SAP

### **7.6.2 Serious Adverse Events**

See Core Safety SAP

### **7.6.3 Adverse Events Leading to Discontinuation of Study Therapy**

See Core Safety SAP

### **7.6.4 Adverse Events Leading to Dose Modification**

See Core Safety SAP

### **7.6.5 Adverse Events**

See Core Safety SAP

### **7.6.6 Select Adverse Events**

See Core Safety SAP with the exception that most of the analyses of select adverse events will be limited to the 30 days safety windows and will not be repeated with the 100 days safety windows. Plots of time to onset of select adverse events and tables of rates by timepoint of select adverse events will not be produced. Summary of any select, drug-related select, select endocrine, drug-related select endocrine AE by worst CTC grade will be produced. Summary of any select, drug-related select, select endocrine and drug-related select endocrine AE leading to discontinuation by worst CTC grade will also be produced.

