- e) Subject Re-enrollment: This study permits the re-enrollment of a subject that has discontinued the study as a pre-treatment failure (ie, subject has not been randomized / has not been treated). If re-enrolled, the subject must be re-consented.

3. Physical and Laboratory Test Finding

Screening laboratory values must meet the following criteria and should be obtained within 14 days prior to first dose:

- i) Absolute Neutrophil Count $\geq 750/\mu\text{L}$ (no WBC growth factors for prior 14 days)
- ii) Platelets $\geq 50 \times 10^3/\mu\text{L}$ (no platelet transfusions for prior 14 days)
- iii) Hemoglobin ≥ 8.5 g/dL (no RBC transfusions for prior 7 days)
- iv) Serum creatinine ≤ 1.5 x ULN or creatinine clearance (CrCl) ≥ 40 ml/min (measured using the Cockcroft-Gault formula below):

$$\text{Female CrCl} = \frac{(140 - \text{age in years}) \times \text{weight in kg} \times 0.85}{72 \times \text{serum creatinine in mg/dL}}$$

$$\text{Male CrCl} = \frac{(140 - \text{age in years}) \times \text{weight in kg} \times 1.00}{72 \times \text{serum creatinine in mg/dL}}$$

- v) AST/ALT ≤ 3 x ULN
- vi) Total Bilirubin ≤ 1.5 x ULN (except subjects with Gilbert's Syndrome, who can have total bilirubin < 3.0 mg/dL).

4. Age and Reproductive Status

- a) Men and women ≥ 18 years of age.
- b) Women of childbearing potential (WOCBP) must have a negative serum or urine pregnancy test (minimum sensitivity 25 IU/L or equivalent units of HCG) within 24 hours prior to the start of study drug.
- c) Women must not be breastfeeding
- d) WOCBP must agree to follow instructions for method(s) of contraception from the time of enrollment for the duration of treatment with nivolumab plus 5 half-lives of nivolumab plus 30 days (duration of ovulatory cycle) for a total of 23 weeks post treatment completion.
- e) Men who are sexually active with WOCBP must agree to follow instructions for method(s) of contraception for the duration of treatment with nivolumab plus 5 half-lives of nivolumab plus 90 days (duration of sperm turnover) for a total of 31 weeks post-treatment completion.
- f) Azoospermic males and WOCBP who are continuously not heterosexually active are exempt from contraceptive requirements. However they must still undergo pregnancy testing as described in these sections

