6.1.1 Serious Adverse Event Collection and Reporting

Following the subject's written consent to participate in the study, all SAEs, whether related or not related to study drug, must be collected, including those thought to be associated with protocol-specified procedures. All SAEs must be collected that occur during the screening period and within 100 days of discontinuation of dosing. If applicable, SAEs must be collected that relate to any later protocol-specified procedure (eg, a follow-up skin biopsy).

The investigator should report any SAE that occurs after these time periods and that is believed to be related to study drug or protocol-specified procedure.

An SAE report should be completed for any event where doubt exists regarding its seriousness.

If the investigator believes that an SAE is not related to study drug, but is potentially related to the conditions of the study (such as withdrawal of previous therapy or a complication of a study procedure), the relationship should be specified in the narrative section of the SAE Report Form.

SAEs, whether related or not related to study drug, and pregnancies must be reported to BMS (or designee) within 24 hours. SAEs must be recorded on the SAE Report Form; pregnancies on a Pregnancy Surveillance Form (electronic or paper forms). When using paper forms, the reports are to be transmitted via email or confirmed facsimile (fax) transmission to:

SAE Email Address: Refer to Contact Information list.

SAE Facsimile Number: Refer to Contact Information list.

For studies capturing SAEs through electronic data capture (EDC), electronic submission is the required method for reporting. The paper forms should be used and submitted immediately, only in the event the electronic system is unavailable for transmission. When paper forms are used, the original paper forms are to remain on site.

SAE Telephone Contact (required for SAE and pregnancy reporting): Refer to Contact Information list.

If only limited information is initially available, follow-up reports are required. (Note: Follow-up SAE reports should include the same investigator term(s) initially reported.)

If an ongoing SAE changes in its intensity or relationship to study drug or if new information becomes available, a follow-up SAE report should be sent within 24 hours to the BMS (or designee) using the same procedure used for transmitting the initial SAE report.

All SAEs should be followed to resolution or stabilization.

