6.2.1 Nonserious Adverse Event Collection and Reporting

The collection of nonserious AE information should begin at initiation of study drug. Nonserious AE information should also be collected from the start of a placebo lead-in period or other observational period intended to establish a baseline status for the subjects.

Nonserious AEs should be followed to resolution or stabilization, or reported as SAEs if they become serious (see [Section 6.1.1](#)). Follow-up is also required for nonserious AEs that cause interruption or discontinuation of study drug and for those present at the end of study treatment as appropriate. All identified nonserious AEs must be recorded and described on the nonserious AE page of the CRF (paper or electronic).

All nonserious adverse events (not only those deemed to be treatment-related) should be collected continuously during the treatment period and for a minimum of 100 days following the last dose of study treatment.

Completion of supplemental CRFs may be requested for AEs and/or laboratory abnormalities that are reported/identified during the course of the study.

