### **7.6.15 Immune-mediated Adverse Events Analysis**

IMAE analyses will include events, regardless of causality, occurring within 100 days of the last dose. These analyses are limited to subjects who received immunosuppressive medication for treatment of the event, with the exception of endocrine events (hypothyroidism/thyroiditis, hyperthyroidism, hypophysitis, diabetes mellitus, adrenal insufficiency), which will be included in the analysis regardless of treatment since these events are often managed without immunosuppression.

IMAEs, serious IMAEs, IMAEs leading to discontinuation, and IMAEs leading to dose delay or reduction will be summarized by worst CTC grade and presented by IMAE Category/PT.

Time to onset, time to resolution, time to resolution with completion of immunosuppressive medication will be defined and summarized by IMAE category in the same manner as for select AEs (see [Section 7.6.6](#)) except that, other than for the endocrine category, the longest duration of IMAEs has to be associated with the use of an immune-modulating medication. Time to Resolution for Longest Any Grade or Grade 3-5 IMAE cluster per subject will be listed.

Use of immune-modulating medications for IMAE management will be summarized by IMAE category in a similar manner as for the select AEs (see [Section 7.6.7](#)).

IMAE rechallenge will be also summarized.

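### Most select-AE analyses stop at 30 days after last dose although AEs are collected for 100, so late non-endocrine select AEs not treated with immunosuppression may appear in no select-AE or immune-mediated table

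*SAP*

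**What the plan says.** **Collection.** Protocol 6.2.1 states that all nonserious AEs, related or not, "should be collected continuously during the treatment period and for a minimum of 100 days following the last dose of study treatment". Protocol 6.1.1 requires SAEs to be collected from screening and "within 100 days of discontinuation of dosing".

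**Select AEs.** SAP 7.6.6 follows the Core Safety SAP with an exception: "most of the analyses of select adverse events will be limited to the 30 days safety windows", with no repeat at 100 days. The same section then lists tables: "Summary of any select, drug-related select, select endocrine, drug-related select endocrine AE by worst CTC grade will be produced". A matching set is listed for events leading to discontinuation. Neither list has a window attached. The two select-AE tables planned for the interim analysis (SAP 7.10) are 30-day only.

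**IMAEs.** SAP 7.6.15 uses a 100-day window regardless of causality, but "These analyses are limited to subjects who received immunosuppressive medication for treatment of the event". Endocrine events (hypothyroidism/thyroiditis, hyperthyroidism, hypophysitis, diabetes mellitus, adrenal insufficiency) are exempt and count whether treated or not.

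**Other events of special interest (OESI).** SAP 7.6.16 reports these in both windows, as categories additional to select AEs and IMAEs.

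**General rule.** SAP 6.1.2 counts an AE as on-treatment up to 30 or 100 days after last dose, depending on the analysis, and refers to the Core SAP.

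**The concern.** The study collects 100 days of post-dose AE data, and for most select-AE analyses the SAP then drops the last 70. The natural reply is that late immune toxicity is reported through the IMAE tables. That reply is incomplete, because entry to those tables depends on how the event was treated. A late non-endocrine event that was only observed, or was managed without immunosuppression, does not qualify.

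The treatment of related event classes is also uneven. IMAEs get 100 days and OESI get both windows, while select AEs mostly get 30 days, and no reason is stated. At stake is the completeness of the late-toxicity profile in the class tables that a safety reader would consult. The primary endpoint is not affected.

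**Working it through.** The plan gives no figure to reproduce here. The check compares windows and follows each kind of late event through the tables.

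**1. Days left out.** Collection runs to at least day 100 after last dose (Protocol 6.1.1, 6.2.1). The select-AE cut-off is day 30. Days 31-100 are 100 - 30 = 70 days.

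**2. Should the data exist?** Protocol Table 5.1-3 puts follow-up visit X01 at day 35 (±7) after last dose and X02 80 days (±7) after X01.
- Nominal X02: 35 + 80 = day 115.
- Earliest: 28 + 73 = day 101. Latest: 42 + 87 = day 129.

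Even the earliest permitted X02 falls after day 100, and Protocol 5.3 asks for in-person toxicity assessment at both visits. The visits therefore span the collection period. Nominal X01 (day 35) itself falls after the 30-day cut-off.

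**3. Where a select AE with onset on days 31-100 is reported.**

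| Late select AE | 100-day IMAE tables (SAP 7.6.15) | Select-AE tables (SAP 7.6.6) |
|---|---|---|
| Endocrine, among the listed types | Yes, treated or not | Outside most |
| Non-endocrine, given immunosuppression | Yes, if the term is in an IMAE category | Outside most |
| Non-endocrine, no immunosuppression | No | Outside most; shown only if an unnamed analysis keeps 100 days |

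The OESI tables do not fill the third row by design, because they are defined as additional categories. The gap is confined to that row.

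**4. Does exposure continue beyond day 30?** Protocol 3.3.1 sets contraception for women at 5 half-lives plus 30 days, "for a total of 23 weeks post treatment completion", and for men at 5 half-lives plus 90 days, 31 weeks in total.
- Women: 23 × 7 = 161 days; half-life = (161 - 30)/5 = 26.2 days.
- Men: 31 × 7 = 217 days; half-life = (217 - 90)/5 = 25.4 days.

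The two differ slightly, as totals in whole weeks would allow. Assuming simple exponential decline, the fraction remaining at day 30 is 2^(-30/half-life):
- 2^(-30/26.2) = 0.45
- 2^(-30/25.4) = 0.44

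So about 44-45% of drug remains when the select-AE window closes. This shows continuing exposure; it is not an estimate of missed events.

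**5. Number of events affected.** This would need a rate of late-onset, non-endocrine select AEs managed without immunosuppression. The documents give none, so it cannot be computed.

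**The case against.** **The SAP says *most*, not all.** The worst-grade summaries listed in SAP 7.6.6 have no window attached and could be the ones kept at 100 days. The Core Safety SAP, which would settle this and define the select-AE categories, is not supplied. This stands: a reader might infer that these late events appear in no select-AE table at all, and the documents do not show that. It does not remove the point, because this SAP never names the analyses that keep 100 days.

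**Endocrine events are covered.** A reader might infer that every late select AE managed without immunosuppression is lost. SAP 7.6.15 includes the listed endocrine events to 100 days regardless of treatment, so the gap is non-endocrine only. This stands in full.

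**Late events are reported elsewhere.** SAP 7.6.1 to 7.6.5 follow the Core Safety SAP without the 30-day exception, and SAP 6.1.2 allows 100-day analyses. Late events may therefore appear in general AE, SAE or discontinuation tables. The version 2.1 history lists the 7.6.6 change together with the new IMAE and OESI sections, which is consistent with a deliberate move of 100-day reporting into those sections. This is fair, but the immunosuppression condition still leaves one class of event outside the new IMAE section.

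**The drug-level argument does not size the gap.** It is tempting to go further. If onset risk followed drug level, the share of post-dose onsets within 100 days that fall after day 30 would be (0.45 - 0.07)/(1 - 0.07) = 0.41 at a half-life of 26.2 days, where 0.07 is the fraction left at day 100; under constant risk it would be 70%. The documents support neither risk shape. Both figures also refer to all post-dose onsets, not to the narrow class at issue, and they omit onsets during treatment. In a worst-grade table, a late event changes a subject's count only if it is the first in its category or exceeds an earlier grade. The objection is right, and these figures should not be used as the size of the problem.

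**A 30-day table is correct for what it states, and late events may reflect subsequent therapy.** Both are true. They are reasons to keep the 30-day tables, not reasons to omit the 100-day ones.

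**Conclusion.** The point holds as a limited reporting gap. Most select-AE analyses omit 70 of the 100 post-dose collection days, and non-endocrine select AEs with onset on days 31-100 and no immunosuppression are outside the 100-day IMAE tables. They may be in no select-AE table, though they may still be visible in general AE tables.

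The conclusion rests on the supplied text of SAP 7.6.6, 7.6.15 and 7.6.16. Two things remain open because the Core Safety SAP is not available: which select-AE analyses keep the 100-day window, and which terms count as select AEs. The number of events is unknown and could be very small. The half-life of about 25-26 days, with 44-45% of drug remaining at day 30 under exponential decline, supports looking beyond day 30 and nothing more. The text does not support a claim of total omission or of a quantified understatement of incidence. This is a cheap improvement worth making.

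**What to change.** In SAP 7.6.6:

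- Produce the worst-grade incidence summaries of any and drug-related select AEs, and of those leading to discontinuation, by category with the 100-day window beside the 30-day window.
- Name the select-AE analyses that remain 30-day only.
- Treat 100-day endocrine select-AE tables as optional, since 7.6.15 already covers the listed endocrine events to 100 days.

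The cost is rerunning the same summaries with a second window and a few more tables. No new data, visits or design change is needed. Because some late events may reflect subsequent therapy, the 30-day tables should be kept so that the two windows can be read together.
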